4.1.3 Communication Strategy

There will be review of available safety, PK and occupancy data (see Section 4.1.2) prior to initiation of the next dose. A Dose Selection Meeting will be conducted between the Sponsor study team, the PET specialist and Investigator prior to dosing of the next cohort. There will be at least one week between each dose level in order to permit adequate time for collation and review of emerging data before the next dose is administered.

4.2 SCIENTIFIC RATIONALE FOR STUDY DESIGN

The study rationale is provided in Section 2.1.

4.2.1 Rationale for Study Population

The participants of this study are healthy male and female (*women of non-childbearing potential*) participants aged 23 to 55 years (inclusive), chosen because of the absence of confounding diseases, which will enable a clearer and more consistent assessment of drug disposition, biological activity and safety profile. In addition, healthy participants are unlikely to require concomitant medications which could interfere with study drugs.

4.2.2 Rationale for PK sampling

Blood samples for determination of RO7017773 in plasma will be collected prior and just after each on-treatment PET/CT scans to inform the PK-RO model.

4.2.4 Rationale for PET Imaging

PET is a non-invasive imaging technique based on the external detection and recording of the decay of positron emitters incorporated in biological molecules introduced in a participant. Molecules of biological interest are labeled with short-lived positron emitter isotopes of biological nuclei (in this study [¹¹C]), providing radioligands with high specific activity and preserved biochemical properties. The PET instruments make it possible to

obtain time varying three-dimensional maps of the absolute radioactivity concentration distribution. By applying ligand kinetic principles to these PET data, it is then possible to estimate absolute values of the physiological parameters that determine the interactions and fate of the labeled molecule. In humans, radioligands are usually administered in minute amounts (typical mass dose is the low µg range). Because of the low radiation doses that are necessary (<10 mSv), PET can be safely used for clinical research purposes.

4.2.5 Rationale for MRI Imaging

A structural MRI scan of the brain will be acquired for each participant to provide an anatomical image to aid PET image analysis.

4.3 DOSE JUSTIFICATION

4.4 END OF STUDY DEFINITION

A participant is considered to have completed the study if he/she has completed the safety follow-up visit.

The end of the study is defined as the date when the last participant last observation (LPLO) occurs. LPLO is expected to occur approximately 5 to 10 days after the last participant last dose of RO7017773.

5. STUDY POPULATION

The study population rationale is provided in Section 4.2.1.

The participants of this study are healthy volunteers between 23 and 55 years of age, inclusive, who fulfill all the inclusion criteria listed in Section 5.1.

Prospective approval of protocol deviations from recruitment and enrollment criteria, also known as protocol waivers or exemptions, is not permitted.

5.1 INCLUSION CRITERIA

Informed Consent

 Able and willing to provide written informed consent and to comply with the study protocol according to ICH and local regulations.

Age

2. Healthy participants aged 23 to 55 years of age, inclusive, at the time of signing the informed consent.

Type of Participants and Disease Characteristics

3. Healthy, as judged by the Investigator.

Healthy status is defined by absence of evidence of any active or chronic disease following a detailed medical and surgical history, a complete physical examination including vital signs, 12-lead ECG, hematology, blood chemistry, serology and urinalysis.

Weight

4. Body Mass Index (BMI) of 18 to 30 kg/m², inclusive at screening.

Sex

- 5. Male and female participants
- a) Female Participants

b) Male Participants

During the treatment period and for at least 90 days after the last dose of study drug, agreement to:

- Remain abstinent (refrain from heterosexual intercourse) or use contraceptive
 measures such as a condom, with partners who are women of childbearing potential
 (WOCBP, as defined in Section 1 of Appendix 5), or pregnant female partners, to
 avoid exposing the embryo to study treatment.
- Refrain from donating sperm for 90 days after the last dose.

The contraception and abstinence requirements are intended to prevent exposure of an embryo to the study treatment. The reliability of sexual abstinence for male and/or female enrollment eligibility needs to be evaluated in relation to the duration of the clinical study and the preferred and usual lifestyle of the participant. Periodic abstinence and withdrawal are not acceptable methods of contraception.

5.2 EXCLUSION CRITERIA

Participants are excluded from the study if any of the following criteria apply:

Medical Conditions

- Any condition or disease detected during the medical interview/physical examination that would render the participant unsuitable for the study, place the participant at undue risk or interfere with the ability of the participant to complete the study, as determined by the Investigator.
- History or evidence of any medical condition potentially altering the absorption, metabolism or elimination of drugs. This includes a surgical history of the gastrointestinal tract affecting gastric motility or altering the gastrointestinal tract.
- History of any clinically significant gastrointestinal, renal, hepatic, bronchopulmonary, neurological, psychiatric, cardiovascular, endocrinological, hematological or allergic disease, metabolic disorder, hypofertility, cancer or cirrhosis.

- History of convulsions (other than benign febrile convulsions of childhood) including epilepsy, or personal history of significant cerebral trauma or CNS infections (e.g., meningitis).
- Clinically significant abnormal finding from the MRI performed after the initial screening examination.
- A history of clinically significant hypersensitivity (e.g., drugs, excipients) or allergic reactions.
- 7. Any major illness within one month before the screening examination or any febrile illness within one week prior to screening and up to first study drug administration.
- Abnormal blood pressure, i.e, systolic blood pressure (SBP) greater than 140 or less than 90 mm Hg, and diastolic blood pressure (DBP) greater than 90 or less than 50 mm Hg.
- 9. Abnormal pulse rate, resting pulse rate greater than 100 or less than 40 bpm.
- 10. History or presence of clinically significant ECG abnormalities before study drug administration (e.g., PQ/PR interval > 210 ms, QTcF > 450 ms (> 470 ms females) or cardiovascular disease (e.g., cardiac insufficiency, coronary artery disease, cardiomyopathy, congestive heart failure, family history of congenital long QT syndrome, family history of sudden death).
- 11. Clinically significant abnormalities in laboratory test results (including hepatic and renal panels, complete blood count, chemistry panel and urinalysis). In the case of uncertain or questionable results, tests performed during screening may be repeated before randomization to confirm eligibility.
- 12. Participants who, in the Investigator's judgment, pose a suicidal or homicidal risk, or any participant with a history of suicidal or homicidal attempts.

Prior/Concomitant Therapy

 Participants likely to need concomitant medication during the study period (including for dental conditions).

Prior/Concurrent Clinical Study Experience

- 14. Participation in an investigational drug or device study within 90 days prior to screening, as calculated from the day of follow-up from the previous study, or more than 4 times a year.
- Previous inclusion in a research and/or medical protocol involving PET or radiological investigations (within the last 12 months).

Diagnostic Assessments

- Positive test for drugs of abuse or alcohol.
- 17. For WONCBP, a positive pregnancy test.
- Show evidence of human immunodeficiency virus (HIV) infection and/or positive human HIV antibodies.

 Positive result on hepatitis B (HBV) or hepatitis C (HCV), presence of hepatitis B surface antigen (HBsAg) or positive hepatitis C antibody test result at screening or within 3 months prior to starting study treatment.

Other Exclusions

- 20. Dietary restrictions that would prohibit the consumption of standardized meals.
- Any suspicion or history of alcohol abuse and/or suspicion of regular consumption of drug of abuse or previous history of or treatment for a dependence disorder.
- 22. Participants who regularly smoke more than 5 cigarettes daily or equivalent and unable or unwilling not to smoke during the in-house period (see Section 5.3.2).
- Participants who have donated over 500 mL of blood or blood products or had significant blood loss within 3 months prior to screening.
- 24. Participants under judicial supervision, guardianship or curatorship.
- 25. Presence of a cardiac pacemaker or other electronic device; ferromagnetic metal foreign bodies in vulnerable positions; presence of certain tattoos that might make it unsafe for an MRI; participant working as a machinist, welder or metal worker; claustrophobia; as assessed by a standard pre MRI questionnaire.
- 26. Occupational radiation exposure or radiation Exposure exposure from medical diagnostic or treatments to ionising radiation in medical research over the past 12 months, that would result in a dose in excess of 10 mSv which when combined with the planned exposure from this study would result in an effective dose in excess of 10 mSv.
- 27. Contraindication for arterial cannulation; Allen's test indicating potential risk in placement of the arterial cannula.

5.3 LIFESTYLE CONSIDERATIONS

5.3.1 Meals and Dietary Restrictions

Participants will have to be fasted for at least 4 hours prior to laboratory safety tests at screening.

5.3.2 Caffeine, Alcohol, and Tobacco

The consumption of food and beverages containing caffeine or other methylxanthine-containing products (e.g., tea, coffee, caffeinated soft drinks, cola, chocolate) will not be permitted from 48 hours before dosing until the end of the residential period. During the period from screening to the follow-up visit when participants are not resident in the unit, participants will be asked to limit coffee or tea consumption to no more than 3 cups per day, and methylxanthine-containing products (e.g. cola and chocolate) must be limited to a maximum of 1 liter per day.

Consumption of alcohol will not be allowed from 48 hours before dosing until the end of the residential period and participants will be asked to limit alcohol to a maximum of 2 units/day (1 unit equates to approximately 330 mL beer, 125 mL of wine or 25 mL of spirits) during the out-clinic period until follow-up. The use of tobacco will not be permitted from 48 hours before dosing until the end of the residential period and participants will be asked to limit tobacco use to a maximum of 5 cigarettes a day or equivalent amount of tobacco during the out-clinic period until follow-up.

5.3.3 Activity

Light ambulatory activities will be permitted, with the level of activities kept as similar as possible on all days in the clinical research unit.

After the participants leave the unit they will be asked to refrain from strenuous physical activity until the end of their participation in the study.

5.4 SCREEN FAILURES

Screen failures are defined as participants who consent to participate in the clinical study but are not subsequently randomized to study treatment/entered in the study.

The Investigator will maintain a screening log to record details of all participants screened and to confirm eligibility or record reasons for screening failure.

Individuals who do not meet the criteria for participation in this study (screen failure) will not be re-screened unless agreed with the Sponsor. A repeat of a screening laboratory test because of a borderline result is not considered a re-screening.

5.5 RECRUITMENT PROCEDURES

Participants will be identified for potential recruitment using pre-screening enrollment logs, clinical database and IEC/IRB approved newspaper/radio/social-media advertisements prior to consenting to take place on this study.

6. TREATMENTS

Study treatment is defined as any investigational treatment(s), marketed product(s), placebo, or medical device(s) intended to be administered to a study participant according to the study protocol.

All IMPs required for completion of this study (RO7017773) will be provided by the Sponsor. All study drug administration will be administered at the study center under supervision of site staff. The radiolabeled PET tracer [11C]Ro15-4513 is considered as non-IMP.

At the start of each PET/CT scan, participants will receive an IV dose of [11C]Ro15-4513.

6.2 PREPARATION/HANDLING/STORAGE/ACCOUNTABILITY

Study drug RO7017773 packaging will be overseen by the Roche clinical trial supplies department and bear a label with the identification required by local law, the protocol number, drug identification and dosage.

The packaging and labeling of the study medication will be in accordance with Roche standard and local regulations.

The investigational site will acknowledge receipt of IMPs and confirm the shipment condition and content. Any damaged shipments will be replaced.

Upon arrival of the IMPs at the site, site personnel will complete the following:

- Check the IMP (RO7017773) for damage.
- Verify proper identity, quantity, integrity of seals and temperature conditions.
- Report any deviations or product complaints to the Monitor upon discovery.

The qualified individual responsible for dispensing the study treatment will prepare the correct dose according to the randomization schedule and Pharmacy Manual.

The Investigator or delegate must confirm that the appropriate temperature conditions have been maintained during transit for all study treatment received and any discrepancies are to be reported and resolved before use of the study treatment.

Only participants enrolled in the study may receive study treatment and only authorized site staff may supply or administer study treatment. All study treatments must be stored in a secure, environmentally controlled, and monitored (manual or automated) area in accordance with the labeled storage conditions with access limited to the Investigator and authorized site staff.

The Investigator, Institution, or the Head of the Medical Institution (where applicable) is responsible for study treatment accountability, reconciliation, and record maintenance (i.e., receipt, reconciliation and final disposition records).

IMPs will either be disposed of at the study site according to the study site's institutional standard operating procedure (SOP) or returned to the Sponsor with the appropriate documentation. The site's method of IMP destruction must be agreed upon by the Sponsor. Local or institutional regulations may require immediate destruction of used IMP for safety reasons. The site must obtain written authorization from the Sponsor before any IMP is destroyed, and IMP destruction must be documented on the appropriate form.

Further guidance and information for the final disposition of unused study treatment are provided in the Pharmacy Manual.

6.3 MEASURES TO MINIMIZE BIAS: RANDOMIZATION AND BLINDING

6.3.1 Method of Treatment Assignment

The study is open-label. Up to 15 healthy participants will be enrolled in this study. The participant numbers will be allocated sequentially in the order in which the participants are enrolled. The randomization numbers will be generated by the Sponsor or its designee and it will be sent to the Investigator.

6.3.2 Blinding

This is an open label study, blinding procedures are not applicable.

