The potential risks for any healthy participants due to the treatment of RO7017773 or study-related procedures are considered minimal and are outweighed by the potential to develop a new treatment for ASD. Further information about the known and expected benefits in the context of potential risks and reasonably expected adverse events of RO7017773 is provided in the Investigator's Brochure (RO7017773 Investigator's Brochure).

3. OBJECTIVES AND ENDPOINTS

The objectives and corresponding endpoints are provided in Table 4.

Table 4 Objectives and Endpoints

	Objectives	Endpoints				
Pri	mary					
•	To assess the relationship between RO7017773 plasma concentration and brain occupancy of GABA _A receptor subtypes (containing the $\alpha 5$ subunit) after single oral doses of RO7017773 using [11 C]Ro15-4513 PET tracer.	•	Occupancy of brain α 5-containing GABA _A receptors by RO7017773 in selected regions of interest (ROIs). RO7017773 plasma concentrations.			
Sec	condary					
•	To assess the safety and tolerability of	•	Incidence and severity of AE.			
	single oral doses of RO7017773.	•	Changes in vital signs, physical findings, ECG parameters, and clinical laboratory results during and following RO7017773 administration.			

		Objectives	Endpoints					
Terti	iary/Explora	atory						
•			•		Ĩ			

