9.3 POPULATIONS FOR ANALYSES

For purposes of analysis, the following populations are defined in Table 7.

Table 7 Analysis Populations

Population	Description
Safety	All participants randomized to study treatment and who received at least one dose of the study treatment, whether prematurely withdrawn from the study or not, will be included in the safety analysis.
PK	All participants who have received at least one dose of study treatment and who have data from at least one post-dose sample will be included in the PK analysis population. Participants will be excluded from the PK analysis population if they significantly violate the inclusion or exclusion criteria, deviate significantly from the protocol, or if data are unavailable or incomplete which may influence the PK analysis. Excluded cases will be documented together with the reason for exclusion. All decisions on exclusions from the analysis will be made prior to database closure.
PK/PD	All participants who received at least one on-treatment PET/CT scan. Participants will be excluded from the PK/PD analysis population if they significantly violate the inclusion or exclusion criteria or deviate significantly from the protocol. Participants will also be excluded if unavailable or incomplete data significantly affect the PK/PD analysis. Excluded cases will be documented together with the reason for exclusion. All decisions on exclusions from the analysis will be made before database lock.

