9.4.3 Pharmacokinetic Analyses

PK concentration data will be summarized using the PK Population, see Table 7.

Individual plasma concentrations of RO7017773 will be listed and summarized. Formal PK analysis will not be done.

9.4.4 Pharmacodynamic Analyses

Pharmacodynamic analysis will be done using the PK/PD Analysis Population, see Table 7.

[figure not shown]
Occupancy of $\alpha 5$ -containing GABA_A receptors by RO7017773 will be calculated for target ROIs. ROIs will be regions with strong [11 C]Ro15-4513 signal (i.e. regions with relatively high density of GABA_A $\alpha 5$ and appreciable size) and including, but not limited to the amygdala, hippocampus, insular cortex, anterior cingulate, and ventral striatum.

Structural MRI image will be co-registered to a standard reference space. A template brain image and associated atlas will be nonlinearly warped to each participant's MRI to enable automated definition of ROIs. Dynamic PET images will be registered to each participant's MRI scan and corrected for motion using a frame-to-frame registration process with a normalized mutual information cost function. ROIs defined on the MRI images will be applied to the dynamic PET data to derive regional time-activity curves (TACs) for ROIs. The total volume of distribution (V_T) for each ROI will be derived and used to calculate RO by RO7017773:

RO and regional V_T data will be presented by listings and no formal statistical analysis will be performed.

Additional PD analyses will be conducted as appropriate.

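### Section 6.3.2 waives blinding without limiting the waiver to treatment administration, and no readable text keeps plasma concentration, dose or scan time from whoever derives V_T

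*Combined protocol and SAP*

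**What the plan says.** Section 6.3 is the protocol's section on measures against bias. Its blinding subsection, 6.3.2, says only: "This is an open label study, blinding procedures are not applicable". It draws no line between giving study drug openly and analysing the images.

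Table 4 in Section 3 lists two primary endpoints: occupancy of α5-containing GABA-A receptors in selected regions of interest (ROIs), and plasma concentration. Section 9.4.4 explains how occupancy arises: V_T "for each ROI will be derived and used to calculate RO by RO7017773". The formula that follows is not visible in the public text.

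Section 9.4.4 automates two steps. A template atlas is warped to each participant's MRI "to enable automated definition of ROIs", and the dynamic images are "corrected for motion using a frame-to-frame registration process with a normalized mutual information cost function". It leaves the list of regions open: "including, but not limited to the amygdala, hippocampus, insular cortex, anterior cingulate, and ventral striatum". Section 9.3 adds a judgement-based exclusion: "Participants will also be excluded if unavailable or incomplete data significantly affect the PK/PD analysis". Those exclusions must be settled before database lock.

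On the flow of data, Section 4.1.2 has the investigator, the PET specialist and the sponsor review occupancy, PK and PK-occupancy data before the next dose level is chosen. Section 4.1.3 adds: "A Dose Selection Meeting will be conducted between the Sponsor study team, the PET specialist and Investigator prior to dosing of the next cohort".

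**The concern.** Open-label dosing is the only reason given for the waiver, and it does not carry over to image quantification. V_T can be derived from scans whose dose, timing and plasma concentration are withheld, even when participant and investigator know all three.

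The data are few: at most 15 participants, with 2 to 3 per dose level (Section 9.2). They have to support a model of occupancy against concentration. If someone who has already seen the concentrations makes a discretionary choice about a region, a frame, a fit or an exclusion, the points may move toward the curve that person expects. The fit would then look better than it is. Because the design is adaptive, the same values also inform the choice of the next dose.

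**Working it through.** **1. Is there masking anywhere in the readable text?** Section 8.8.1 (PET/CT scans) covers acquisition and does not mention coding. Section 9.4.4 covers processing and does not mention who is masked to what. Section 9.3 requires exclusions to be decided before database lock, but does not say that those deciding are unaware of occupancy, dose or concentration. Under Sections 4.1.2 and 4.1.3, occupancy and PK data will have been reviewed cohort by cohort well before that lock. No readable passage states the order in which V_T is derived and concentrations are released within a cohort.

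**2. Where can judgement enter?** ROI outlines and motion correction are algorithmic. What remains is the open-ended region list (9.4.4), PK/PD exclusions (9.3), any rejection of scans or frames, and any choice of kinetic fit. The readable text neither fixes nor forbids the last two.

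**3. How many scans?** Each participant has one baseline and two on-treatment scans (Section 4.1). The maximum is 15 × 3 = 45 scans, of which 15 × 2 = 30 are on-treatment.

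**4. How sensitive is occupancy to V_T?** The plan states no figure, so there is none to reproduce. The following rests on assumptions.

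Let V_ND be non-displaceable binding, and assume occupancy = (V_T,base − V_T,on) / (V_T,base − V_ND). A relative shift e in on-treatment V_T moves occupancy by e × V_T,on / (V_T,base − V_ND). With V_T,base = 1, V_ND = f and true occupancy R, V_T,on = 1 − R(1 − f). For e = 5%, in percentage points:

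| True occupancy | f = 0 | f = 0.2 | f = 0.4 |
|---|---|---|---|
| 20% | 4.0 | 5.25 | 7.3 |
| 50% | 2.5 | 3.75 | 5.8 |
| 80% | 1.0 | 2.25 | 4.3 |

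For example, at R = 20% and f = 0.4, V_T,on = 0.88 and 0.05 × 0.88 / 0.6 = 0.073. For e = 2% the range is 0.4 to 2.9 points.

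**5. What does that do to EC50?** Take f = 0 and a simple Emax curve with maximum 100% and slope 1, so that EC50 = C(1 − R)/R at concentration C. If on-treatment V_T is lowered by a fraction s, then R' = 1 − (1 − s)(1 − R), and the EC50 implied by that single point is multiplied by [(1 − R')/R'] / [(1 − R)/R]:

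| R | R' at s = 5% | Ratio, s = 3% | Ratio, s = 5% | Ratio, s = 10% |
|---|---|---|---|---|
| 20% | 24% | 0.866 | 0.792 | 0.643 |
| 50% | 52.5% | 0.942 | 0.905 | 0.818 |
| 80% | 81% | 0.963 | 0.938 | 0.878 |

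At s = 5%, the implied EC50 falls by about 21%, 9.5% and 6%. Low-occupancy points are the most sensitive.

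**The case against.** **Coding scans would not hide the dose.** Cohorts of two run in sequence, apparently at one dose each, and that dose is agreed at a meeting the PET specialist attends. Baseline and on-treatment sessions can also be told apart by date. This stands. Coding with a lock mainly protects against knowledge of plasma concentration, with partial cover for scan time.

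**The PET specialist may not be the analyst.** A reader might infer from Section 4.1.3 that the person who quantifies the scans helps to choose the dose. No section says who derives V_T, and Section 2.3 places scanning at a separate imaging center. Nor does any section say that concentrations reach the analyst first. The supported statement is that nothing readable prevents either.

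**The missing rule may exist in unreadable text.** The occupancy formula in 9.4.4, all of 9.4.5, Sections 8.6 and 8.7, and Appendix 6 are not visible. A fixed kinetic model or a masking rule may be there. This stands as a caveat. If a masking rule does exist, the unqualified sentence in 6.3.2 conflicts with it and should still be narrowed.

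**The sensitivity figures are not bias estimates.** A reader might take the EC50 falls as the expected damage. The documents give no V_T error and no evidence of analyst bias. Bias toward an expected curve would raise some points and lower others, whereas the calculation lowers V_T throughout. It also concerns one isolated point, not a fit to as many as 30 on-treatment scans. This stands in full.

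**The stakes are limited.** The study tests no hypothesis (9.1), occupancy and V_T are only listed (9.4.4), and dose choice also rests on safety and tolerability data (4.1.2). This lowers the priority of the point but does not remove it, because the values still feed the exposure-occupancy relationship named in the primary objective.

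**Conclusion.** The point holds in a limited form. The waiver in 6.3.2 is broader than its reason, and no readable text keeps concentration, dose or scan time from whoever derives V_T. Automated ROI definition and motion correction narrow the room for bias to the four places listed in step 2 of the working.

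The size of any bias cannot be derived from the documents. The sensitivity of 1.0 to 7.3 percentage points for a 5% shift in V_T assumes the occupancy formula shown, V_ND between 0 and 40% of baseline V_T, and true occupancy between 20% and 80%. The EC50 ratios further assume no non-displaceable binding and a simple Emax curve reaching 100%.

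Two stronger readings are tempting. One is that the occupancy results will be biased; nothing in the documents shows that. The other is that such bias could never be found. Appendix 1 counts instrument data and magnetic media among source records (Section 2.1.2) and requires records to be kept for at least 15 years (Section 2.2). If the dynamic PET data are kept on that basis, a masked analyst could re-quantify them. Dose choices already made could not be undone. The point is a worthwhile, cheap improvement and does not put the study's validity in question.

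**What to change.** Amend Section 6.3.2 so that open label refers to treatment administration only, and add the following for PET quantification:

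- The existing PET laboratory works on coded scans.
- Any scan or frame rejection is recorded with its reason at that stage.
- Regional V_T for the cohort is locked with a time stamp before plasma concentrations and dose are merged for the Dose Selection Meeting.
- Where existing staff allow, V_T is derived by someone who does not attend that meeting.

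A useful complement, if unreadable text does not already provide it, is to fix the ROI list, the kinetic model and the scan-rejection rules in advance. Exclusions that rest on PK data cannot be masked in this way and would still need documented reasons.

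The cost is file coding for at most 45 scans and a short lock step per cohort, with no extra scan or reader. The documents give no cost figure, so calling this cheap is a judgement. Section 4.1.3 already sets aside at least one week between dose levels for collating and reviewing data. The limitation to state openly is that masking to dose stays partial.
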